#### 4.3 Test Article: Clinical Development

The research paper (Reference 15) is a technical evaluation of the xenon delivery system and the use of inhaled xenon in an *in-vivo* laboratory model that replicated the human clinical scenario of; global hypoxic ischemic insult in a neonate followed by cooling (the standard treatment) and concurrent xenon administration. It describes the early clinical development and performance of the delivery system and is attached in full as Appendix A2.

Reference:	CH
Issue:	2
Revision:	3
Issue Date:	1 May 2013
Page	30 of 49

Appendix 5 summarises the data obtained when this breathing system design was used in our recent 14 baby human neonatal feasibility/safety study.

#### 4.3.1 Proof-of-Concept Pre-clinical Studies

Following the technical feasibility study [15] above, physiological data has been obtained by the research group in a much larger laboratory experiment over 5 years in neonatal piglets who were subjected to a previously described global hypoxic-ischemic insult, resuscitated, and then randomised to receive varying combinations and durations of cooling and xenon. The xenon delivery system used for this large pre-clinical study was the same as the one proposed for the clinical feasibility study.

This pre-clinical study has also been published as a paper:

*Xenon enhances hypothermic neuroprotection in asphyxiated newborn pigs. Chakkarapani E, Dingley J, Liu X, Hoque N, Aquilina K, Porter H, [name] M. Ann Neurol. 2010 Sep;68(3):330-41.[15]*

Additional details on the conduct of this laboratory pre-clinical study are given in Appendix 5 and a large quantity of physiological data is also supplied in this appendix demonstrating the physiological effects of cooling alone and then combinations of xenon + cooling in neonatal pigs after this severe global hypoxic-ischaemic insult.

#### 4.3.2 Proof-of-Concept Clinical study

In March 2011 this research group successfully completed a clinical feasibility/safety study of inhaled xenon in combination with cooling using this equipment design to deliver xenon in 14 human neonates.

A large quantity of physiological data was acquired and this is presented in Appendix 5.

#### 4.4 Test Article: Regulatory Status

The Neonatal Xenon Breathing Device is not CE marked in Europe and will therefore any UK clinical study involving its use will require review by, and approval from, the UK Competent Authority, the Medicines and Healthcare products Regulatory Agency (MHRA). Ethical approval for the study will be obtained from the appropriate Research Ethics Committee (REC) prior to commencement.

#### 4.5 Test Article: Packaging and Labelling

The Neonatal Xenon Breathing Device requires no packaging and will be clearly labelled in compliance with the requirements of the EU Medical Devices Directive. Devices used in any clinical trial will clearly be marked "Exclusively For Clinical Investigations".

#### 4.7 Control/Comparator Therapy

This is a randomised comparative pilot study. The control group will receive the standard treatment for this condition which is whole body cooling for 72 h as it would be unethical to withhold the normal treatment from the control group. The treatment group (experimental group) will also receive an identical cooling regime but in addition will receive 50% xenon within 5h of age in the breathing gas mixture via the NXBD breathing circuit for a period of 18h.

#### 5.0 Patient Selection

Potential study participants will be identified via the existing identification system used at St Michaels for administration of their (standard) cooling regime for the region.

Clinical Study Protocol	Reference:	CH
Neonatal Xenon Breathing Study (CoolXenon2 Study)	Issue:	2
	Revision:	3
	Issue Date:	1 May 2013
	Page	31 of 49

There is good evidence that the earlier cooling (now standard treatment) is started, the greater the ultimate benefit. Consequently neonates are often allowed to passively cool during retrieval to Bristol, where active cooling is then continued, in a bid to start the process as early as possible. This argument is also likely to be true for xenon and there is *in-vivo* laboratory data to support this. Parents of potential participants in study therefore need to be approached as early as possible after birth if their baby meets entry criteria for the study.

Therefore they will first be approached by a trained medical member of the clinical team. This person will briefly explain the study to the parents of the neonate with the aid of the information sheet, and later a member of the team will obtain written consent where this has been agreed.

Informed written consent will be obtained from a parent (only the mother can consent if parents are not married) after a full verbal and written explanation of the study by a named physician or trained nurse such as an advanced nurse practitioner. Such staff will also meet with parents during the intervention period to ensure that they understand the study procedures and continue to consent to participate in the study. Information can be given by local trained staff and consent can also be taken over the phone with the mother if she is unable to be available for the consent process (e.g. cannot be moved shortly after Caesarean Section).

Approval for the study is being obtained from the Regional South West Research Ethics Committee covering St Michael's Hospital.

Most of the patients will be born outside the study hospital (Outborn). Outborn patients are estimated to be >90% of patients. They are brought to the hospital by a dedicated retrieval team and ambulance from Bristol.

The local delivery hospitals will have medical staff (e.g. consultants, specialist registrars, advanced nurse practitioners) trained in consenting for the CoolXenon2 trial. A training log with signatures, a short CV and competency approval will be kept centrally.

Parents will receive a written information leaflet (1 page, short version) when the infant is eligible for cooling treatment. Staff will discuss CoolXenon2 with parents as soon as practically possible. Parents will be able to speak on the phone to a member of the treatment team if they need further information and help with the consent process. Parents will also be offered the opportunity to speak to members of the treatment team that are picking up the baby for transport.

Trained staff on the transport team can take consent for the study.

A more detailed information sheet regarding the trial will be given to parents after the first conversation or at the earliest suitable time.

#### Which of the parents can consent to letting the child enter the trial?

- Either parent if they are married
- If the parents are not married, only the mother can consent - provided she is awake and understanding (eg not under the influence of anaesthetic drugs)
- If the mother is not in a state to understand the situation (and the parents are living together but are not married) the father can consent on behalf of the mother. The consent process must be repeated with the mother as soon as she is able to understand the child's condition.

A parent who is eligible to consent can, at any time and without a specific reason, withdraw the child from the study. In this situation, xenon treatment will then be stopped as soon as possible and medically safe (within minutes).

#### **5.1 Inclusion Criteria**

Patients meeting the following criteria will be considered eligible for the study:

Infants will be eligible for inclusion in this study if the St Michael's hospital standard inclusion criteria for cooling are met and additional inclusion criteria for xenon administration are met.

#### **St Michael's hospital standard inclusion criteria for cooling**

Standard Hypothermia Treatment Criteria for 72 hrs of cooling — all of criteria A, B, and C.

A Infants > 36.0 weeks gestation (clinical assessment) with at least ONE of the following:

- 1 Apgar score <5 at ten (10) minutes after birth

Reference:	CH
Issue:	2
Revision:	3
Issue Date:	1 May 2013
Page	32 of 49

2      Continued need for resuscitation, including endotracheal or mask ventilation, at ten minutes after birth

3      Acidosis defined as either umbilical cord pH or any arterial, venous or capillary pH within 60 minutes of birth less than pH 7.00

4      Base deficit greater than or equal to 16 mmol/L in umbilical cord blood sample or any blood sample within 60 minutes of birth (arterial or venous blood). If the infant meets criterion A then assess for neurological abnormality using criterion B and C (by trained personnel):

B      Moderate or Severe encephalopathy as evidenced by any of the following --

1      Altered state of consciousness (reduced or absent responses or pathological irritability and hyper responsive and at least ONE or more of the following:

2      Hypotonia

3      Abnormal reflexes including oculomotor or pupillary abnormalities

4      Absent or weak suck

5      Clinical seizures, as recorded by trained personnel

*And*

C      At least 30 minutes duration of amplitude-integrated electroencephalography (aEEG) recording that shows abnormal background aEEG activity. The decision to cool is based on the worst section of the aEEG, not the best (al Naqeeb, et al, 1999) or seizures (clinical or electrical) thus meeting ONE of the following:

1      Normal background with some electrical seizure activity

2      Moderately abnormal activity (upper margin of trace >10µV and lower margin <5µV)

3      Suppressed activity (upper margin of trace <10µV and lower margin of trace <5µV)

4      Definite seizure activity

#### **Additional inclusion criteria for xenon**

Before being considered for additional inhaled xenon therapy via the breathing gas mixture, the infant would need to meet further additional entry criteria (all must be met):

- 1)      Intubated, ventilated, sedated, being cooled.
- 2)      <5 hours old
- 3)      Any seizures under control.
- 4)      Weight > 2nd centile for gestational age
- 5)      Stable cardiovascular parameters; Mean arterial pressure >40mmHg.
- 6)      Oxygen requirement via mechanical ventilator < 40%.
- 7)      Positive End Expiratory Pressure (PEEP) requirement < 6cm H2O
- 8)      Arterial/capillary/venous pCO2 <7.0kPa (ideally arterial). Venous can be higher if peri-arrest and tissues have been very recently ischaemic
- 9)      Postnatal age <5 hours
- 10)     Absence of major congenital abnormalities, imperforate anus and in particular any bowel obstruction, congenital abnormalities suggestive of chromosomal anomaly or other syndromes that include brain dysgenesis. Neonates with congenital syndromes affecting the brain should be excluded when diagnosed (see exclusion criteria below)

#### **5.2     Exclusion Criteria**

##### **Exclusion criteria for cooling**

1.      Infants expected to be greater than 5 hours of age at the time of starting cooling treatment.
2.      Futility. Where prognosis is considered to be hopeless e.g. no cardiac output for 20 minutes.

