Patient Population	Newborn infants $\geq$ 36 weeks gestation which satisfy all St Michael's Hospital standard inclusion criteria for cooling (i.e. at risk of brain injury following poor condition at birth) and which additionally satisfy the inclusion criteria of this investigation for the administration of xenon by inhalation. Cooling should be started within 3h of age and xenon within 5. Use of a shorter treatment delay in these entry criteria will optimize the possibility of finding an effect if there is one.
Population Size	16 babies in each of 2 groups
Structure	Single centre prospective randomised clinical pilot study
Duration of Participation	Xenon administration period of 18 hours. Recruitment period up to 18 months from start of study. Short and long term monitoring until 18 months of age. Therefore total study duration 3 years.
Method of Assignment	Comparative study. Neonates meeting all entry criteria can be included.
Randomisation	Patients will be randomised between cooling (standard treatment) and xenon+cooling groups as this is a comparative study. Patients will be randomised on a 1:1 basis to receive either conventional cooling therapy or cooling plus xenon therapy.

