## Overview

The proposed study is planned to be a single centre study at St. Michael's Hospital Bristol, prospective randomised pilot clinical study. It may include Southmead Hospital Bristol at a later stage if recruitment is low. We have included a shorter delay for recruitment to optimize the effectiveness of hypothermia and potentially xenon. We will accept cooled infants that are <3h old and start xenon within 5h of age. In an experimental study we did not find any improvement of adding xenon if both were started at 5 hours after the insult [6], however 2h delayed xenon when HT was started immediately was more effective than HT alone [7].

The study examines the effect of inhaled xenon gas used in the treatment of newborn infants with hypoxic-ischemic encephalopathy (HIE), in combination with cooling which is the standard treatment for this condition. The hypothesis is that the xenon+cooling combination will produce better neuroprotection than the standard treatment, cooling, alone. Xenon, a rare anaesthetic gas, is almost side-effect free and shows great promise as a method of enhancing the neuroprotection offered by cooling. It is, however, extremely expensive at £25-50/L.

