We propose to study 32 full term infants with moderate or severe HIE who, on clinical grounds, require mechanical ventilation and hypothermia for 72 hours. The hypothermia (cooling) will be routinely applied if the standard existing criteria for this are met except recruitment needs to be earlier, <3h rather than 6h as noted above. Candidates for the study will be randomly assigned to one of two groups: (i) the standard treatment for this condition, 72 hours of cooling, *i.e. the treatment they are already receiving*, or (ii) addition of 50% xenon concentration in the breathing gas from the mechanical ventilator for 18 hours in combination with the existing cooling regime, the cooling then continuing to 72 hours. All efforts will be made to commence delivery of the xenon and cooling as soon as possible after birth, with maximum delay of 5 hours for xenon and 3 hours for cooling. Xenon will be given in the breathing gas mixture via a special delivery system situated between the ventilator and airway of the infant. This device has been specifically developed to eliminate xenon wastage [8], without which this putative therapy would be completely unfeasible on cost grounds. It has recently been successfully used in 14 babies with the same entry criteria in our recent MHRA approved human feasibility/safety study [9]. Meetings of an independent Data Review Group will take place after the recruitment of every 4th baby during enrolment of infants to the xenon+cooling group.

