## 2.0 Objectives

The aim of this study is to examine using primarily short term measures and secondarily long term outcomes, the potential neuroprotective effects of the cooling+xenon combination when compared to cooling alone. We will examine the feasibility of recruiting earlier than previous trials, <3h for HT and <5h for starting xenon and assess what proportion of the eligible infants we can recruit. We will compare the short term biomarkers (aEEG recovery, MRI score, LDH and time to full feeds) in the two groups with those obtained previously in our randomised dataset (infants from CoolCap and TOBY) as well as the large group cooled since 1/12/2006 under the same protocol. In these groups of children we have both short term markers as well as Bayley outcome and have shown that our combined biomarkers has a PPV of 93%.

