**Eligibility**  
 Meet inclusion and exclusion criteria  
 This includes  
 ≥36.0 weeks gestational age  
 Expectation of being able to start cooling at ≤3h age and, if required  
 Xe at ≤5h age.

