#### Exclusion criteria for cooling in the CoolXenon2 study

1. Infants expected to be greater than 3 hours of age at the time of starting cooling treatment.
2. Futility. Where prognosis is considered to be hopeless e.g. no cardiac output for 20 minutes.

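### Section 5.2 sets the cooling-start exclusion at 5 hours; section 3.1 and every other statement of the limit say 3 hours

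*Protocol*

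**What the plan says.** The protocol gives the eligibility criteria twice, once in section 3.1 (Study design and procedures) and once in section 5 (Patient Selection). Item 1 of the cooling exclusions differs between them:

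- Section 3.1, cooling exclusions for this study: "Infants expected to be greater than 3 hours of age at the time of starting cooling treatment".
- Section 5.2, cooling exclusions: "Infants expected to be greater than 5 hours of age at the time of starting cooling treatment".

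Elsewhere the two limits are kept apart, 3 hours for cooling and 5 hours for xenon. The Summary (Patient Population) says "Cooling should be started within 3h of age and xenon within 5". The Overview says "We will accept cooled infants that are <3h old and start xenon within 5h of age", and later "with maximum delay of 5 hours for xenon and 3 hours for cooling". Section 2.0 says "We will examine the feasibility of recruiting earlier than previous trials, <3h for HT and <5h for starting xenon". The Eligibility box of the flow chart in section 3.0 says "Expectation of being able to start cooling at ≤3h age and, if required". The Randomisation and Clinical management parts of section 3.1 and the design justification in section 3.3 also give 3 hours.

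**The concern.** This is an operative entry criterion, and its two versions classify the same infant differently. Section 5 is the formal patient selection section, and section 5.1 defines eligibility without referring back to section 3.1. A screener working from section 5 alone finds no 3-hour limit on the start of cooling.

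Two things are at stake. First, section 9.1 makes the feasibility of early recruitment the main purpose, and section 2.0 plans to report what proportion of eligible infants can be recruited. If eligibility has two definitions, that proportion has two possible denominators. Second, the short delay is a deliberate design feature. The Summary justifies it as giving the best chance of seeing an effect, and the Overview reports an experimental study in which adding xenon brought no improvement when both treatments began 5 hours after the insult. Section 5 as written admits infants whose cooling and xenon both begin close to 5 hours of age.

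**Working it through.** The protocol gives no calculated figure on this point, so the check is a comparison of texts.

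**Step 1. Every statement of the cooling limit.**

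| Place | Cooling limit | Kind of statement |
|---|---|---|
| Summary, Patient Population | 3 h | start of cooling |
| Overview, first paragraph | 3 h | age at acceptance |
| Overview, third paragraph | 3 h | recruitment age and start of cooling |
| 2.0 Objectives | 3 h | recruitment aim |
| 3.0 flow chart, Eligibility | 3 h | start of cooling, eligibility rule |
| 3.1 cooling exclusions, item 1 | 3 h | start of cooling, exclusion rule |
| 3.1 Randomisation | 3 h | start of cooling, target maximum |
| 3.1 Clinical management | 3 h | start of cooling |
| 3.3 Justification of Design | 3 h | recruitment aim |
| 5.2 cooling exclusions, item 1 | **5 h** | start of cooling, exclusion rule |

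Nine places give 3 hours (six outside section 3.1 and three inside it) and one gives 5 hours. Only the flow chart and the two exclusion items are worded as eligibility rules, and the section 3.1 exclusion alone is enough to establish the contradiction. The other entries show which number was intended.

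**Step 2. Could 5 hours be the hospital's ordinary cooling limit?** No. The Overview describes the study's departure from standard criteria as "except recruitment needs to be earlier, <3h rather than 6h as noted above", so the ordinary figure there is 6 hours. Five hours matches neither the ordinary limit nor the study's cooling limit. It matches the xenon limit, which suggests that the xenon figure was carried into the cooling criterion.

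**Step 3. Does anything else in section 5 restore 3 hours?** No. The standard cooling criteria in section 5.1 give no age at the start of cooling. The additional xenon criteria require the infant to be already undergoing cooling and under 5 hours old, without saying when cooling must have begun. The effective limit in section 5 is therefore just under 5 hours.

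**Step 4. A test case.** Take an infant first cooled at 3.5 hours who meets all other criteria before 5 hours.

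- Section 5.2, item 1: 3.5 < 5, not excluded. Section 5.1: being cooled and under 5 hours old, passes.
- Section 3.1, item 1: 3.5 > 3, excluded. The flow chart condition also fails.

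**Step 5. Size.**

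- Gap between the limits: 5 − 3 = 2 hours, and 2/3 = 67% longer than intended.
- Weight of one such infant in the planned sample: 16 + 16 = 32, and 1/32 = 3.1%.
- Start times to check: 8 + 7 = 15 infants recruited by April 2013 (Summary, Statistical Analysis; section 3.3 also refers to the first 15). If the two xenon starts reported since then are additional, 15 + 2 = 17.

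The number of infants actually first cooled between 3 and 5 hours cannot be derived from the protocol.

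**The case against.** The strongest reply concerns weight, since the two sentences plainly conflict. Exclusions accumulate, so a reader of the whole protocol would still exclude an infant first cooled at 3.5 hours, because section 3.1 says so under a heading specific to this study. The intended value is not in doubt. The practical window is also narrower than 3 to 5 hours: intubation, sedation, seizure control, at least 30 minutes of aEEG, consent, randomisation and the start of xenon must all fit before 5 hours. Local hospitals typically call within 1 hour (section 7.3), passive cooling counts as a start, and section 3.1 says retrieved infants are always cooled before transfer. The criterion applies before randomisation and the analysis is descriptive, so no bias between arms follows.

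Most of this stands, and it limits the size of the problem. It does not remove it. Section 3.1 also provides for active cooling to begin only when the transport team arrives, so the window is not shown to be empty. More than 90% of infants are expected to be outborn, and trained local or transport staff may take consent, so clear criteria away from the base hospital matter. The reply that section 13.5 already requires eligibility to be verifiable from the file, and that section 13.7 provides source data verification, helps only if the check uses the right limit. A check against section 5.2 would pass an infant first cooled at 3.5 hours.

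**Conclusion.** The concern holds. Section 5.2 item 1 carries the wrong number: it contradicts the same criterion in section 3.1 and all other statements of the cooling limit, and section 5 contains nothing that corrects it. Read alone, section 5 extends the permitted cooling start by up to 2 hours.

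The conclusion rests on the current protocol text alone. Its practical effect rests on an assumption the protocol neither supports nor rules out, namely that someone screens from section 5 without consulting section 3.1. The number of infants affected may be small or zero, and no distortion of the comparison between arms is claimed. The point should be fixed because it concerns an entry threshold on which the main feasibility question depends.

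**What to change.** 1. In section 5.2, cooling exclusions, item 1, change 5 hours to 3 hours.
2. Keep one full eligibility list and replace the other with a cross-reference, so that the two cannot diverge again.
3. Check the cooling start time of every infant enrolled so far (at least 15, or at least 17 if the two later xenon starts are additional) and flag any that began after 3 hours.
4. Report feasibility against both limits explicitly: 3 hours for cooling and 5 hours for xenon.

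The cost is one number and one cross-reference in a wording amendment, approved as section 11.0 requires, plus a short review of records. No extra patients or procedures are needed.
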